3.3.2 Asthma Control Questionnaire (ACQ-5)

In the ACQ-5 questionnaire the patients are asked to recall the status of their asthma during the previous week with regards to symptoms, see [Section 3.2](#) for specific questions.

The ACQ-5 questions will be measured on a 7-point scale scored from 0 (totally controlled) to 6 (severely uncontrolled). The ACQ-5 score is computed as the un-weighted mean of the responses. If response to any of the questions is missing, the ACQ-5 score will be set to missing by the ePRO provider. If ACQ-5 reaches a value of 1.5 or more, the patient is reported as having loss of asthma control.

As mentioned above, the ACQ is based on 5-item version. The ACQ-5 will be self-administered within the ePRO once weekly during the study.

The outcome variable for ACQ-5 is a weekly average.

3.3.3 Asthma daily diary score

Asthma symptoms during night-time and daytime will be recorded by the patient each morning and evening in the Asthma Daily Diary. Symptoms will be recorded using a scale 0-3, where 0 indicates no asthma symptoms. The outcome variables, asthma symptom daytime score (recorded in the evening), night-time score (recorded in the morning), and total score will be calculated and presented separately.

The outcome variable Asthma Daily Diary total score will be calculated by taking the sum of the night-time and daytime asthma symptom scores recorded each day. The outcome variable Asthma Daily Diary total weekly mean for a specific week will be calculated as the sum of non-missing daily total is divided by the number of non-missing days of that week. If a patient is missing a value for either night-time or daytime asthma symptom score on a given day, then the total score for that day will be set to missing.

Example for Asthma Daily Diary total weekly mean calculation:

| | Day 1 | Day 2 | Day 3 | Day 4 | Day 5 | Day 6 | Day 7 | Day 8 |
|---------|--|--------------------------------|--------------------------------|--------------------------------|--------------------------------|--------------------------------|--------------------------------|--------------------------------|
| Morning | Prior randomisation night-time scores (D1_M) | Day 1 night-time scores (D2_M) | Day 2 night-time scores (D3_M) | Day 3 night-time scores (D4_M) | Day 4 night-time scores (D5_M) | Day 5 night-time scores (D6_M) | Day 6 night-time scores (D7_M) | Day 7 night-time scores (D8_M) |
| Evening | Daytime scores on Day 1 (D1_E) | Day 2 daytime scores (D2_E) | Day 3 daytime scores (D3_E) | Day 4 daytime scores (D4_E) | Day 5 daytime scores (D5_E) | Day 6 daytime scores (D6_E) | Day 7 daytime scores (D7_E) | Day 8 daytime scores (D8_E) |

Total daily scores for each day is defined as: $D(n)_E + D(n+1)_M$, where $n = 1, 2, \dots, 7$

Week 1 morning mean, $W1_M$,: $(D2_M + \dots + D8_M) / 7$. “/7” is for illustration in this example, the number of non-missing days will be used in the analysis.

Week 1 evening mean, $W1_E$, is defined as: $(D1_E + \dots + D7_E) / 7$. “/7” is for illustration in this example, the number of non-missing days will be used in the analysis.

Total daily scores on a weekly basis should be $[D(n)_E + D(n+1)_M] / 7$ where $n = 1, \dots, 7$. “/7” is for illustration in this example. The number of non-missing number of days will be used in the analysis.

The number of asthma symptom-free days will be calculated for each patient as the total number of days in the 52 week treatment period where the total asthma symptom score is 0. The outcome variable proportion of asthma symptom-free days will be calculated using the total number of days with completed asthma symptom score diary during the 52-week treatment period as the denominator.

Summary statistics will be presented by treatment and week for the number of asthma symptom-free days and the proportion of asthma symptom-free days. The handling of missing data in the calculation of weekly average daytime asthma daily diary score, weekly average night-time asthma daily diary score and weekly average total asthma daily diary score is described in [Section 3.1.5](#).

3.3.4 Time to moderate or severe exacerbation

Severe exacerbation is defined as a worsening in asthma symptoms and

- Use of systemic corticosteroids for at least three days and/or
- An unscheduled visit or emergency room visit due to asthma symptoms that requires at least one dose of systemic corticosteroids and/or

- An in-patient hospitalization due to asthma requiring at least one dose of systemic corticosteroids.

Moderate exacerbation is defined as a temporary increase in maintenance therapy in order to prevent a severe event supported by a sustained (≥ 2 day) worsening in at least one key control metric i.e. asthma score, reliever medication use, night time awakening or morning PEF.

The start and stop dates of severe exacerbations experienced by a patient during the treatment period will be derived from the following rule.

- The start date of a severe exacerbation is defined as the start date of systemic corticosteroids or increased use of systemic corticosteroids or of emergency room visit or hospital admission, whichever occurs first.
- The stop date is defined as the last day of systemic corticosteroids/increased use of systemic corticosteroids or hospital discharge, whichever occurs last.

The start and stop dates of moderate exacerbations experienced by a patient during the treatment period will be derived from the following rule.

- The start date of a moderate exacerbation is defined as the first day of increase in temporary maintenance therapy.
- The stop date is defined as the last day of this treatment.

The EXACA module of the eCRF will be used to derive the severe exacerbation variable. The MED1 module of the eCRF will be used to derive the moderate exacerbation variable.

Time to a moderate or severe exacerbation will be censored at 52-weeks for patients who do not experience a moderate or severe exacerbation during the 52-week study period or at the time point after which a moderate or severe exacerbation experience could not be assessed (for lost-to-follow-up patients). For patients who withdraw from the study without reporting a moderate or severe exacerbation, time will be censored at the date of withdrawal, if known, else at the patient's last clinical visit plus one day.

As defined for the primary analysis, exacerbations that occur after a subject has discontinued IP but before maximum follow-up time will still be accounted when deriving the total number of exacerbations. Likewise, the follow-up time will reflect the follow-up time regardless of whether or not the subject is still on IP.

3.3.5 Proportion of subjects with 1 moderate or severe exacerbation during 52-weeks of treatment

The proportion of patients who experience 1 moderate or severe exacerbation during the 52-weeks of treatment will be a supportive measurement to the primary objective. The outcome variable will categorize each patient as having one moderate or severe exacerbation experience being met or not (yes=1/no=0).

The proportion of such patients will be calculated for each treatment group as:

Number of patients with 1 moderate or severe exacerbation during the 52-week treatment period/ number of patients in treatment group

3.3.6 Reliever medication use

The number of rescue medication inhalations taken will be recorded by the patient in the Asthma Daily Diary twice daily. The number taken at daytime lung function assessments will be recorded in the evening. The number of inhalations taken at night-time lung function assessments will be recorded in the morning. Reliever medication usage is captured in the daily diary as the number of inhaler puffs.

The number of inhalations (puffs) per day will be calculated as follows:

Number of night inhaler puffs + number of day inhaler puffs

The outcome variable total weekly mean reliever medication use for a specific week will be calculated the same way as total weekly Asthma Daily Diary scores in [Section 3.3.3](#), i.e. Day 1 should be D1_E+D2_M, and the weekly mean is (D1 total +D2 total+...+D7 total)/ non-missing number of days.

3.3.7 FEV₁ pre/post BD

The pre/post BD FEV₁ will be determined by the spirometry tests at the clinic at each visit as scheduled. To ensure quality control all spirometry measurements are reviewed to ensure that they meet ATS/ERS (American Thoracic Society 2000) criteria for acceptability. Section 5.1.2 of the CSP contains further details of the spirometry recordings.

The endpoints are:

- 1) absolute change from baseline in pre-BD FEV₁ (L)
- 2) percentage change from baseline in pre-BD FEV₁
- 3) absolute change from baseline in post-BD FEV₁ (L)
- 4) percentage change from baseline in post-BD FEV₁

The absolute changes from baseline are the main FEV₁ endpoints. The percentage changes from baseline are supportive endpoints.

A reversibility test will be performed at Visit 1 (Week -4), with spirometry assessment 30±10 minutes before and after administration of short-acting β₂ agonist.

The percent reversibility is calculated as follows:

Reversibility (%) = (FEV₁ post – FEV₁ pre) / FEV₁ pre x 100

The value of Percent predicted normal for FEV₁ used as part of the eligibility process will not be checked programmatically.

3.3.8 Peak Expiratory Flow (PEF)

Morning and evening PEF measurements will be taken at home on the ePRO device by the patient on a daily basis and then averaged over the week. The outcome variable is weekly average total PEF. The weekly morning PEF average for Week 1 is calculated as (D2_M+...+D8_M)/non-missing days) and weekly evening PEF average is calculated as (D1_E+...+D7_E)/non-missing days). Weekly average total PEF is calculated as the average of the weekly morning mean and the weekly evening mean. The handling of missing data is described in [Section 3.1.5](#).

3.3.9 Fractional Exhaled Nitric Oxide (FeNO)

FeNO measurements will be taken at home by patients every second day. FeNO measurements will also be taken at designated time points at the study centre.

The home FeNO outcome variable is a weekly average FeNO based on the average of measurements taken at home for a specific week. The handling of missing data in the calculation of weekly average FeNO is described in [Section 3.1.5](#).

The home FeNO outcome variable will be separate to the clinic FeNO outcome variable.

3.3.10 Vital Capacity and Forced Expiratory Flow at 25-75%

FVC and FEF25-75 are spirometry measurements taken pre- and post- BD at clinic visits 1 (Week -4), 2 (Week 0), 6 (Week 4), 9 (Week 7), 14 (Week 12), 15 (Week 13), 16 (Week 16), 17 (Week 20), 18 (Week 28), 19 (Week 36) and 21 (Week 52).

Summary statistics will also be presented for each treatment group at the specified visits.

3.3.11 Night time awakenings

Night-time awakenings due to asthma symptoms will be recorded by the patient in the Asthma Daily Diary each morning by answering the question whether he/she woke up during the night due to asthma symptoms by a “yes” or “no” response.

Summary statistics will also be presented for each treatment group at each week.

The outcome variable is a weekly mean calculated as the number of times the subject answered ‘yes’ over a period of 7 sequential days. The first weekly mean (the treatment weekly mean) will be based on the morning recording on Day 2 up to and including the morning recording on Day 8. The second weekly mean (the follow-up weekly mean) will be based on the morning recording on Day 9 up to and including the morning recording on Day 15 and so on.

3.4 Calculation or derivation of safety variable(s)

The following safety data will be collected: vital signs, physical examination (include assessment of the following: general appearance, respiratory, cardiovascular, abdomen, skin, head and neck(including ears, eyes, nose and throat) lymph nodes, thyroid, musculoskeletal (including spine and extremities) and neurological systems, 12-lead ECG, haematology, clinical chemistry, urinalysis, DLco, PEFr and reported adverse events (AEs).

Change from baseline (Visit 2) to each post-baseline time point where scheduled assessments were made will be calculated for relevant measurements.

3.4.1 Adverse events

The definitions of adverse events (AEs) and serious adverse events (SAEs) are given in Sections 6.1 and 6.2 of the CSP.

All AEs recorded in the eCRF will be coded according to the terminology of the latest version of the Medical Dictionary for Regulatory Activities (MedDRA).

All adverse events will be listed for each patient and summarised by treatment actually received. Treatment-emergent AEs will be tabulated (number and percentage of patients) by system organ class (SOC), preferred term (PT), intensity and relation to study medication.

Any AE occurring before the start of study treatment will be included in the data listings but will not be included in the summary tables of AEs and excluded from safety analysis set.

If an AE has a missing onset date then unless the stop date of the AE indicates otherwise, this will be considered 'on-treatment'. Similarly, if an AE has a partial onset date, then unless the partial onset date or the stop date indicates otherwise, this will be considered 'on-treatment'.

AE data will be categorized according to their onset date into the following periods:

- AEs starting during pre-treatment (onset date \geq Visit 1 (Week -4) and before the first dose of IP)
- AEs starting during study (onset date \geq the first day of IP and \leq Visit 21 (Week 52))
- AEs starting during ICS + LABA treatment period (onset date \geq the first day of IP and $<$ Visit8 (Week 6))
- AEs starting during ICS taper down period (onset date \geq Visit 8 (Week 6) and $<$ Visit 11 (Week 9))
- AEs starting during remainder of study (onset date \geq Visit 11 (Week 9) \leq Visit 21 (Week 52))

The timing of AEs will be assigned to the period in which they first started. The same during treatment definition will be used for laboratory and physical examination data, where applicable. Note, not all Exacerbations will be recorded as AEs.

Common AEs, AEs with outcome of death, SAE, DAEs and Flu-like AEs will be summarized separately. Flu-like AEs are defined in [Section 4.2.5.1](#).

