Prior to randomization patients will undergo an approximately 2-4 week screening period. Eligible patients will be prescribed their usual controller medication (i.e. ICS + LABA in separate inhalers, in addition to a rescue medication inhaler (short-acting β 2 agonist [SABA]), and issued electronic diaries, peak flow and FeNO meters to record asthma symptoms and lung function during each morning and evening at home. Asthma control will be assessed using the 5-item asthma control questionnaire (ACQ-5) and when patients have shown to be controlled (ACQ-5 \leq 0.75) they are randomized to receive AZD1419 or placebo administered as an inhalation at the clinic once per week.

A withdrawal design will be used where the first 6 doses of IMP will be administered as add-on to the patient's regular ICS + LABA. The controller treatment will then be tapered down during the next 3 doses of AZD1419/placebo and the last 4 doses will be administered during a period of complete withdrawal of maintenance treatment. SABA will be allowed and used as

reliever medication during the whole study. The first 4 doses of IMP will be given as 4mg per week after which the dose is potentially adjusted to 1 mg or 8 mg per week based on frequency and severity of flu-like adverse events (arthralgia, chills, pyrexia, myalgia) occurring within 24h of inhalation in the individual patient.

The patients will be monitored closely with regards to asthma symptoms, reliever use and lung function and upon loss of control of their asthma they will resume their ICS + LABA controller medication and are considered to have met the primary endpoint. The patients are then followed for an additional 4 weeks.

Objectives

Primary Objective:	Outcome Measure:
To assess the efficacy of inhaled AZD1419 in eosinophilic asthma patients after withdrawal of controller treatment of ICS + LABA	Time to loss of asthma control

For the purpose of the study loss of asthma control is defined as any of the following:

- (a) An increase of ACQ-5 to 1.5 or more
- (b) A reduction of 30% or more in morning peak expiratory flow (PEF) from baseline on 2 consecutive days
- (c) At least six additional reliever inhalations of SABA in a 24-hour period relative to baseline on 2 consecutive days
- (d) An exacerbation requiring systemic corticosteroids

Secondary Objective:	Outcome Measure:

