The investigational product, AZD1419 or matching placebo, will be administered once weekly using the commercially available and CE marked I-neb[®] Adaptive Aerosol Delivery [ADD] System from Philips Respironics.

AZD1419/placebo is supplied as a solution at a concentration of 2 mg/mL, 8 mg/mL and 16 mg/mL in phosphate-buffered saline.

Three inhaled dose levels of AZD1419/placebo, 1 mg, 4 mg and 8 mg may be investigated in a 12 week regimen consisting of 4 once weekly inhaled doses of 4 mg followed by 8 weeks of

inhaled doses of 1 mg, 4 mg, or 8 mg. The maximum possible dose that any patient will receive during the study is 8 mg.

The placebo for this trial is phosphate-buffered saline, pH 7.2.

Statistical methods and sample size

The primary efficacy variable is the time to loss of asthma control, and the primary analysis is to compare the time to loss of asthma control for AZD1419 with placebo. The time to loss of control in the AZD1419 group will be compared to that of the placebo group using a log rank test (with accompanying Kaplan-Meier plot). The hypothesis test will be one-sided, with $\alpha=0.05$.

The secondary outcome variables listed above will be analysed longitudinally using all measurements taken over the course of the study. Continuous variables will be modelled using mixed effects models; categorical outcomes will be modelled using generalized estimating equations. Additionally, all outcomes will be summarized by treatment group at each measurement time point.

This trial has about 90% power to yield a statistically significant ($\alpha = 0.05$, 2-sided) difference between the pooled active and placebo groups in time to loss of asthma control given that the cumulative number of controlled subjects at week 52 is 20% and 60% for control versus active respectively. Assuming a drop-out of about 10-15%, this will require about 70 patients in total (32 events).

TABLE OF CONTENTS

PAGE

TITLE PAGE.....	1
VERSION HISTORY	2
PROTOCOL SYNOPSIS	3
TABLE OF CONTENTS	7
1. INTRODUCTION	15
1.1 Background and rationale for conducting this study	15
1.2 Rationale for study design, doses and control groups.....	16
1.3 Benefit/risk and ethical assessment.....	17
1.4 Study Design	19
2. STUDY OBJECTIVES.....	21
2.1 Primary objective	21
2.1.1 Definition of Loss of asthma control	21
2.2 Secondary objectives	21
2.3 Safety objectives	22
2.4 Exploratory objectives	22

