4.2 Treatment period

When patients are comfortable using the prescribed inhalers and have gone through the inclusion/screening assessments the patients may be randomized. An ACQ-5 score of ≤ 0.75 is required for randomization. A total of 70 patients are planned to receive 13 weekly doses of IMP (1:1) during the conduct of the study. Study drug will be administered as a nebulized inhalation (using the I-neb® device (Philips Respironics)) at the clinic. The patients will be observed at the clinic for at least 6 hours after the first dose and for at least 2 hours after the remainder of doses.

Patients will receive placebo or AZD1419 at 4 mg/week for 4 weeks, after which each patient's dose will be maintained or adjusted up or down based on the individual patient's frequency and severity of flu-like AEs (defined in [Section 6.1.1](#)) appearing within 24 hours after dosing, see [Figure 2](#). All decisions are subject to investigator judgment. If an investigator believes that a patient is not tolerating a dose for any reason, the next dose can be reduced independent of the rules described. Further instructions on Dose Adaptation are included in [Section 4.2.2](#).

During the dosing period, patients will have ICS + LABA controller medications tapered down and discontinued. LABA will be stopped on the evening prior to receiving dose 7 (Visit 8), and ICS will then be gradually tapered down and discontinued during the next 3 weeks. The first week after LABA discontinuation, the patients will receive their usual full dose of ICS. The week thereafter the total daily ICS dose will be reduced by 50% and the week thereafter the total daily dose will be reduced to 25% of the patient's usual full dose of ICS. ICS is discontinued in the evening prior to receiving IMP dose 10 (Visit 11). The regimen for tapering down the ICS according to the above guidelines will be decided by the Investigator for the individual patient, i.e. as appropriate the Investigator will adjust the ICS dose down and

potentially change dosing regimen from BID to QD to achieve half and then a quarter of the daily dose of ICS. Patients will be able to use SABA reliever therapy as needed at all times during the study. Reliever use will be monitored on a daily basis in the ePRO device, as a component of asthma control throughout the trial.

For details of all assessments done during the treatment period refer to Section 5 and for timing of the procedures refer to Table 1.

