4.2.2 Dose Adaptation Procedure

Given the well-known potential for flu-like symptoms from TLR9 agonism, dosing for each patient will be adapted based on the individual's flu-like AEs. The flu-like symptoms usually respond well to paracetamol (and otherwise resolve spontaneously within 24-48 hours following dosing), and the dose adaptation should be based on the assessment of flu-like symptoms after intake of paracetamol.

After the first 4 doses an assessment of the individual patient will be performed according to experiences of flu-like AEs (arthralgia, chills, pyrexia, myalgia) within 24h of inhalation, with adaptation of AZD1419 accordingly:

If no or only mild flu-like AEs occur after the first 4 doses, then the subsequent doses will be stepped up to 8 mg.

If any severe flu-like AEs occur after any of the first 4 doses, then the subsequent doses will be stepped down to 1 mg.

Otherwise, the subsequent doses will be maintained at 4 mg.

All patients will continue dosing with placebo or AZD1419 at the adjusted levels until they have received a total of 13 inhaled weekly doses.

[figure not shown]
All dosing decisions are subject to investigator judgment. If an investigator believes that a patient is not tolerating a dose for any reason, the next dose can be reduced independent of the rules described above.

Dosing will be stopped in patients who do not tolerate a 1mg dose and they will be followed for an additional 4 weeks for safety before they discontinue the study.

Since e.g. side effects from influenza vaccination could potentially impact the interpretation of the flu-like symptoms after the dosing of study drug, it is suggested that such vaccination should be performed e.g. 2 days after a dose of IMP.

For definition of severity of AE (including flu-like symptoms), see Section 6.3.3.

Figure 2 Dosing

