7.2 Dose and treatment regimens

7.2.1 Study Treatments

A total of 70 eligible patients will be randomly assigned 1:1 to receive 13 inhaled once weekly doses of either placebo or AZD1419 during the conduct of the study. Study drug will be administered at the clinic. All eligible patients will be taking ICS and LABA during the screening period, with SABA as rescue therapy during the study.

All patients randomized to AZD1419 will have 4 mg/week of AZD1419 or placebo for 4 doses. After the 4th dose, the 5th dose will be adapted based on tolerability for the final 9 doses. Refer to Section 4.2.2 for details of the dose adaptation procedure.

Instructions for the I-neb will be provided by AstraZeneca.

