4.2.3 Exposure and Compliance

Extent of exposure to IP by compliance, total treatment duration by mean daily dose, and recordings on eDiary will be summarized by treatment group and using both the safety analysis set and full analysis set.

The date and time of all IP administrations, and all missed doses will be listed using the safety analysis set.

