Flu-like AE will be displayed as well as the total number of AEs for each preferred term by maximum reported intensity. Separate tables will be presented for each of the following periods: AEs occurring during study, AEs occurring during ICS+LABA treatment period, AEs occurring during ICS taper down period and AEs occurring during remainder of study as defined in [Section 3.4.1](#). A table will also be presented for the AEs occurring during IP only treatment period. This is defined as

- *AEs occurring during IP only treatment period (onset date \geq Visit 11 (Week 9) < Visit 15 (Week 13))*

Flu-like symptoms are defined as events of arthralgia, chills, pyrexia (fever), or myalgia (see section 6.1.1 of protocol).

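### The dose is individualised from dose 5 (Week 4), but no AE summary table separates doses 1-4 from later doses, and no exposure table counts patients or doses at 1, 4 and 8 mg

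*SAP*

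**What the plan says.** **Dosing.** The protocol synopsis states "Three inhaled dose levels of AZD1419/placebo, 1 mg, 4 mg and 8 mg may be investigated" and "The first 4 doses of IMP will be given as 4mg per week after which the dose is potentially adjusted". Under protocol 4.2.2, "If no or only mild flu-like AEs occur after the first 4 doses, then the subsequent doses will be stepped up to 8 mg"; any severe flu-like AE leads to 1 mg, and all other patients stay at 4 mg. Protocol 7.2.1 fixes the timing: "After the 4th dose, the 5th dose will be adapted based on tolerability for the final 9 doses". Protocol 4.2 and 4.2.2 also let the investigator lower the next dose on judgement, outside these rules.

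**Adverse events.** SAP 3.4.1 assigns AEs by onset date to periods defined by controller medication:
- "AEs starting during ICS + LABA treatment period" runs from the first day of IP to before Visit 8 (Week 6).
- The taper period runs from Visit 8 to before Visit 11 (Week 9).
- The remainder runs from Visit 11 to Visit 21 (Week 52).

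For flu-like AEs, SAP 4.2.5.1 says "Separate tables will be presented for each of the following periods". It reuses these periods and the whole-study period, and adds an IP-only period from Visit 11 to before Visit 15 (Week 13). SAP 2.1.3 places every patient with at least one AZD1419 dose in a single active group.

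**Exposure.** SAP 4.2.3 says "Extent of exposure to IP by compliance, total treatment duration by mean daily dose, and recordings on eDiary will be summarized by treatment group". SAP 4.2.3.1 promises counts of patients per category but defines no exposure category, such as dose level. IP administrations are to be listed by date and time.

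**The concern.** Safety and tolerability is a stated objective, and flu-like AEs are the variable that drives each patient's dose. Doses 1-4 are the one stretch in which the randomised arms are compared at a common scheduled level, before anyone has been moved because of how they tolerated it. From dose 5 the active arm mixes patients moved down after a severe event with patients moved up because they had none or only mild ones.

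If the tables never separate these stretches, a flu-like AE rate for the active arm cannot be read as the rate at the starting dose or as the rate under the adapted regimen. Without a count of patients at each level, a reader of the summary tables cannot tell how much experience at 8 mg lies behind any rate. The question is open: the earlier tolerability data came from healthy volunteers dosed once weekly for 4 weeks (protocol 1.2), and protocol 1.3 notes that patients with asthma may react differently.

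**Working it through.** **1. Dose calendar.** Protocol 4.2 ties dose 7 to Visit 8 and dose 10 to Visit 11. SAP Table 6 puts Visit 8 at Week 6 and Visit 6 at Week 4 (target Day 29). So dose *n* falls at Visit *n* + 1, Week *n* - 1, and dose 5 falls at Visit 6, Week 4. The plan's own count reproduces: 4 fixed + 9 adapted = 13 doses.

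**2. Doses per SAP period.**

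| SAP period | Weeks of dosing | Doses | Pre-adaptation | Adapted |
|---|---|---|---|---|
| ICS+LABA | 0-5 | 1-6 | 4 | 2 |
| Taper | 6-8 | 7-9 | 0 | 3 |
| IP-only (dosing part of the remainder) | 9-12 | 10-13 | 0 | 4 |
| Total | | 13 | 4 | 9 |

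In the ICS+LABA period, 2/6 = 33% of doses are post-adaptation. By amount of drug in that period:
- stepped up to 8 mg: 4 x 4 + 2 x 8 = 32 mg, of which 16 (50%) is post-adaptation;
- kept at 4 mg: 16 + 8 = 24 mg, of which 8 (33%);
- stepped down to 1 mg: 16 + 2 = 18 mg, of which 2 (11%).

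**3. Mean daily dose.** The SAP gives no formula for it. I assume total mg divided by the extent of exposure in SAP 4.2.3.1. For 13 weekly doses the extent is 84 + 7 + 1 = 92 days. For a completer who follows the rule:
- 1 mg: 16 + 9 x 1 = 25 mg; 25/92 = 0.27 mg/day
- 4 mg: 16 + 9 x 4 = 52 mg; 52/92 = 0.57 mg/day
- 8 mg: 16 + 9 x 8 = 88 mg; 88/92 = 0.96 mg/day

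These three individual values are distinct. The group mean is not informative in the same way. Take 35 completers in the active arm (half the planned 70; illustrative, since SAP 1.3 reports 81 randomised). If all stay at 4 mg, the total is 35 x 52 = 1820 mg. If 20 go to 1 mg and 15 to 8 mg, it is 20 x 25 + 15 x 88 = 1820 mg. Both give 0.57 mg/day.

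Individual values also blur once histories are irregular:
- A patient stepped up to 8 mg who stops after dose 5 has 24 mg over 28 + 7 + 1 = 36 days, or 0.67 mg/day. That is closer to a 4 mg completer (0.57) than to an 8 mg completer (0.96).
- Four doses at 4 mg, five at 8 mg, then four reduced to 4 mg give 16 + 40 + 16 = 72 mg. Four at 4 mg and seven at 8 mg, with two missed before dose 13, give 16 + 56 = 72 mg. Both are 72/92 = 0.78 mg/day. The second patient's compliance is 11/13 = 85%, so both also fall in the same 80-120% compliance category (SAP 4.2.3.2).

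**4. Effect of a cut at dose 5.** Weeks 0-3 then hold 4 doses, all scheduled at 4 mg or placebo, and Weeks 4-5 hold 2. With 3 in the taper and 4 in the IP-only period, the adapted doses sum to 2 + 3 + 4 = 9, matching protocol 7.2.1.

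**The case against.** A reader might infer that no output at all shows tolerability at 4 mg, or that the report could not say at which dose an AE occurred. The documents do not support that.
- Weekly PEFR is a named safety outcome, and SAP 4.2.4.6 analyses home PEF week by week. The Week 1-4 windows end on the morning of Day 29 or the evening of Day 28, nominally before dose 5 takes effect.
- Pre-dose FEV1 is analysed by visit. Vital signs, taken 15 minutes after dosing in the treatment period, are also summarised by visit. DLco is measured at Week 4, though its timing relative to dose 5 is not stated.
- All data, AEs and IP administrations are listed, so patient-level reconstruction is possible, although the administration listing names date and time, not level.

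The controller-based periods are also not a mistake. Protocol 8.5.9.1 specifies them, and the safety objective refers to the time after controller withdrawal. The trial has no dose-finding objective: it randomises 1:1 and is powered on pooled active against placebo. So it would be wrong to fault the SAP for not supporting a choice of dose. Both arms follow the same titration rule, so the first-period comparison is still a valid randomised comparison of regimens. Leaving dose out of the exposure summary may be deliberate, since the amendment history records that wording on dose was removed from SAP 4.2.3 in August 2018; no reason is given.

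Two further limits stand. Investigator discretion means that doses 1-4 are scheduled, not guaranteed, at 4 mg. Mean daily dose does identify the level for an individual completer who follows the rule; it fails for group means and irregular histories.

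None of this supplies an AE or flu-like AE table before adaptation, or a count by level. PEF, vital signs and DLco do not capture flu-like AEs, and listings do not replace a prespecified summary.

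**Conclusion.** The point holds as a gap in the planned summary tables. The dose becomes individual at Week 4, the AE and flu-like AE periods cut only at Weeks 6, 9 and 13 with all AZD1419 levels pooled, and exposure is reduced to mean daily dose. One third of the doses in the first AE period are post-adaptation, and half the drug for a patient stepped up. No summary table gives patients or doses at 1, 4 and 8 mg.

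This rests on the weekly schedule being kept and, for the exposure figures, on the assumed formula for mean daily dose. The consequence is limited: the primary endpoint, the type I error and the overall treatment-group safety comparison do not change. What is lost is the randomised AE comparison before tolerability selection, and a plain account of who received what. It is a cheap improvement worth making, not a flaw that invalidates the safety analysis.

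**What to change.** Keep the controller-based periods and make these changes to the SAP before unblinding, as protocol section 8 allows.

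1. **SAP 3.4.1 and 4.2.5.1.** Sub-split the ICS+LABA period at dose 5, for AEs and flu-like AEs: (a) first dose to before dose 5, labelled as scheduled 4 mg or placebo with any investigator reductions noted; (b) dose 5 to before Visit 8. Use the actual date and time of dose 5, and state where (a) ends for a patient with no fifth dose (for example, the Visit 6 target, Day 29).
2. **SAP 4.2.3.** Replace mean daily dose with number and percent of patients at each level at dose 5, final level, number of doses at each level, and cumulative mg.
3. **Optional.** Add a flu-like AE table by nominal level for active and matching placebo, using the 24-hour window of protocol 6.1.1. Label it descriptive and non-randomised after dose 4, because level then depends on earlier AEs. Restrict it to flu-like AEs: they are defined in the protocol, whereas a respiratory AE group is not.

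The cost is SAP wording and a few descriptive tables, some with small cells. AE onset date and time (protocol 6.3.3) and IP administration records are already collected. The tables by level assume that those records include the level given. No dosing rule, procedure or primary analysis changes.
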